**Adjunctive Vorapaxar Therapy in Patients with Prior Myocardial Infarction
Treated with New Generation P2Y₁₂ Receptor Inhibitors Prasugrel and Ticagrelor (VORA-
PRATIC): A Prospective, Randomized, Pharmacodynamic Study**

[name], PhD
University of Florida College of Medicine-Jacksonville
[name]
[name]
[contact]
[contact]
E-mail: [contact]

Summary

Dual antiplatelet therapy (DAPT) with aspirin and a P2Y₁₂ receptor inhibitor represents the standard of care for the long-term secondary prevention of atherothrombotic events in patients with myocardial infarction (MI). The novel P2Y₁₂ receptor inhibitors prasugrel and ticagrelor are characterized by more prompt, potent, and predictable antiplatelet effects compared with clopidogrel and are associated with a greater reduction of ischemic events in acute coronary syndrome patients. However, rates of ischemic recurrences remain high, which may be in part due to the fact that other platelet signaling pathways, such as thrombin-induced platelet aggregation, continue to be activated. Vorapaxar is a novel, orally active, competitive and slowly reversible protease-activated receptor (PAR)-1 inhibitor, which exerts potent inhibition of thrombin-mediated platelet aggregation. It is approved for clinical use by the Food and Drug Administration for the reduction of thrombotic cardiovascular events in patients with a history of MI or with peripheral arterial disease. A large-scale clinical trial showed that the use of vorapaxar (2.5 mg once/daily) in addition to standard antiplatelet therapy (including aspirin and a P2Y₁₂ receptor inhibitor) was effective in the secondary prevention of recurrent thrombotic events in patients with previous atherothrombosis, in particular in patients with prior MI, at the expense of an increase in major bleeding. However, to date clinical trial experience with vorapaxar has been almost exclusively with the P2Y₁₂ receptor inhibitor clopidogrel and the effects of vorapaxar in combination with state-of-the-art antiplatelet therapy in the post-MI setting, including prasugrel or ticagrelor, is largely unexplored. This may indeed represent a limitation for the uptake of vorapaxar in modern day clinical practice where these agents are being more broadly utilized. Further, the role of vorapaxar as part of a dual antithrombotic treatment regimen, in addition to a novel P2Y₁₂ receptor inhibitor,

with withdrawal of aspirin, represents another important area of clinical interest as it has the potential to maximize ischemic protection while reducing the risk of bleeding. The proposed prospective, randomized, parallel-design, open label, study conducted in a real world clinical setting of post-MI patients will aim to assess the pharmacodynamic effects of vorapaxar in addition to antiplatelet therapy with a novel P2Y₁₂ receptor inhibitor (prasugrel or ticagrelor) with and without aspirin. Pharmacodynamic assessments will be performed at multiple time points and with different assays exploring multiple pathways of platelet aggregation. Exploratory assessments on the safety of such approach will also be evaluated.

Background and Significance

Dual antiplatelet therapy (DAPT) with aspirin and a P2Y₁₂ receptor inhibitor represents the standard of care for the long-term secondary prevention of atherothrombotic events in patients with myocardial infarction (MI) [1]. Clopidogrel is the most widely used P2Y₁₂ receptor inhibitor and the use of DAPT with aspirin and clopidogrel has consistently demonstrated to reduce the risk of thrombotic recurrences in patients with acute coronary syndrome (ACS) [2]. However, clopidogrel is a prodrug characterized by high interindividual response variability [3]. The novel P2Y₁₂ receptor inhibitors prasugrel and ticagrelor are characterized by more prompt, potent, and predictable antiplatelet effects compared with clopidogrel and are associated with a greater reduction of ischemic events in ACS patients, at the expense of an increase in major bleeding [4,5]. However, despite adequate cyclooxygenase-1 (COX-1) and ADP P2Y₁₂-receptor blockade, rates of ischemic recurrences remain high, which may be in part due to the fact that other platelet signaling pathways, such as thrombin-induced platelet aggregation, continue to be activated and can thus contribute to thrombus formation [2,6,7]. In particular, the serine protease thrombin is one of the most potent platelet activators and the surface of activated platelets is the main source of circulating thrombin, especially following an ACS [6-8]. Vorapaxar is a novel, orally active, highly selective, competitive and slowly reversible protease-activated receptor (PAR)-1 inhibitor, which exerts potent inhibition of thrombin-mediated platelet activation and aggregation [9,10]. After oral administration vorapaxar is rapidly absorbed with high bioavailability (>90%) and is metabolized by cytochrome P450 (CYP) 3A4. Pharmacokinetic studies have shown that vorapaxar has a dissociation half-life as long as 20 hours which leads to consistent pharmacodynamic (PD) effects [9,10]. Importantly, there is an

interplay between purinergic and thrombin mediated platelet signaling pathways which may result in enhanced P2Y₁₂ inhibition when vorapaxar is added to DAPT [11].

Recently, vorapaxar (2.5 mg once daily) has been approved for clinical use by the US Food and Drug Administration (FDA) for the reduction of thrombotic cardiovascular events in patients with a history of MI or with peripheral arterial disease (PAD), and must be used in addition to standard-of-care antiplatelet therapy with aspirin and/or clopidogrel [12]. Vorapaxar has been also approved by the European Medicines Agency for the treatment of patients with previous MI [13]. These indications are largely attributed to the findings of the TRA 2P-TIMI 50 (Thrombin Receptor Antagonist in Secondary Prevention of Atherothrombotic Ischemic Events - Thrombolysis in Myocardial Infarction 50) trial [14]. In particular, the trial showed that the use of vorapaxar (2.5 mg once/daily) in addition to standard antiplatelet therapy [including aspirin (94% of patients), a thienopyridine, or both (DAPT in 58% of patients; the thienopyridine was clopidogrel in 99.3% of patients)] was effective in the secondary prevention of recurrent thrombotic events (cardiovascular death, MI, or stroke) in patients with previous atherothrombosis, in particular in patients with prior MI, at the cost of increased bleeding [14,15]. However, the effects of vorapaxar in combination with state-of-the-art antiplatelet therapy in the post-MI setting, including prasugrel or ticagrelor, is largely unexplored.

Study Rationale

To date clinical trial experience with vorapaxar has been almost exclusively with the P2Y₁₂ receptor inhibitor clopidogrel and the effects of vorapaxar in combination with state-of-the-art antiplatelet therapy in the post-MI setting, including prasugrel or ticagrelor, is largely unexplored.

This may indeed represent a limitation for the uptake of vorapaxar in modern day clinical practice where these agents are being more broadly utilized [1,2]. This knowledge gap represents an important area for exploratory research as it represents how vorapaxar could potentially be used in daily clinical practice. Further, given the potent and comprehensive antiplatelet effects achieved with the novel P2Y₁₂ receptor inhibitors, the role of aspirin when added to these agents have been questioned [16,17]. Prasugrel and ticagrelor are effective in inhibiting both ADP P2Y₁₂-dependent and thromboxane A₂-dependent pathways of platelet aggregation [16,17]. In particular, the platelet inhibition achieved by combining aspirin and a potent P2Y₁₂-receptor blocker was shown to be no greater than that produced by the P2Y₁₂-receptor blocker alone in healthy volunteers [16,17]. Therefore, the role of vorapaxar as part of a dual antithrombotic treatment regimen including prasugrel or ticagrelor and stopping aspirin, represents another important area of clinical interest as it has the potential to maximize ischemic protection while reducing the risk of bleeding.

Study Aims

To assess the pharmacodynamic effects of vorapaxar in addition to antiplatelet therapy with a novel P2Y₁₂ receptor inhibitor (prasugrel or ticagrelor) with and without aspirin in a real-world setting of post-MI patients. Exploratory assessments on the safety will also be evaluated.

Research Plan

Study Population

Inclusion criteria:

1. Patients with a prior MI within the previous 12 months.

2. On DAPT with low-dose aspirin (81mg od) and either prasugrel (10mg od) or ticagrelor (90mg bid) as per standard-of-care.
3. Free from bleeding and ischemic events after the index MI event.
4. Age between 18 and 75 years old.

Exclusion criteria:

1. History of stroke, transient ischemic attack, or intracranial hemorrhage.
2. Active pathological bleeding, history of bleeding events or increased risk of bleeding.
3. Known severe hepatic impairment.
4. Age >75 years.
5. Body weight <60 Kg.
6. Use of strong CYP3A inhibitors (e.g., ketoconazole, itraconazole, posaconazole, clarithromycin, nefazodone, ritonavir, saquinavir, nelfinavir, indinavir, boceprevir, telaprevir, telithromycin and conivaptan) or inducers (e.g., rifampin, carbamazepine, St. John's Wort and phenytoin).
7. On treatment with any oral anticoagulant (vitamin K antagonists, dabigatran, rivaroxaban, apixaban, edoxaban).
8. On treatment with any antiplatelet agent other than aspirin, prasugrel and ticagrelor in the past 14 days.
9. Creatinine clearance <30 mL/minute.
10. Platelet count <80x10⁶/mL
11. Hemoglobin <10g/dL
12. Hemodynamic instability

13. Pregnant females [women of childbearing age must use reliable birth control (i.e. oral contraceptives) while participating in the study].

Research Design

The proposed investigation will be a prospective, randomized, parallel-design, open label, PD study conducted in a real world clinical setting of post-MI patients. Patients will be required to be on DAPT for at least 2 weeks before randomization. Although vorapaxar is approved for use irrespective of the timing of the MI, the rationale for including patients after 2 weeks is that, given the negative results of the clinical trial with vorapaxar in the acute phase of ACS, it may be reasonable to wait until patients have been stabilized after their index MI [18]. The rationale for the exclusion of elderly patients (aged >75 years) and patients with a low body weight (<60 kg) is that prasugrel is generally not recommended in these patient populations [1,2].

[figure not shown]
The study will be performed at the University of Florida Health Science Center at UF Health Jacksonville - Division of Cardiology. Patients will be recruited in the Cardiology Clinics of our institution and will be screened by Cardiology Research staff, who will verify that all candidates meet inclusion and exclusion criteria. Results from blood tests performed within the last 90 days will be considered valid for screening purposes. If these are not available, a blood sample will be collected for the screening phase. Although the study has an open-label design, laboratory personnel performing PD testing will be blinded to treatment assignment.

Patients on DAPT with aspirin and prasugrel/ticagrelor as part of their standard of care for at least 2 weeks and who are meeting study entry criteria will be randomly assigned in a 1:1:1 fashion to one of the following 3 treatment regimens: 1) DAPT (aspirin and prasugrel/ticagrelor) plus

vorapaxar 2.5mg od; 2) prasugrel/ticagrelor plus vorapaxar 2.5mg od; 3) continue DAPT with aspirin and prasugrel/ticagrelor. Randomized treatment will be administered for 30 ± 3 days; prasugrel and ticagrelor will be administered at their standard maintenance dose (10mg od and 90mg bid, respectively). Randomization will be stratified according to type of P2Y₁₂ inhibitor, in order to include at least 35% of patients on prasugrel. The rationale for predicting a higher number of randomized patients on ticagrelor derives from the more broad clinical indications of ticagrelor compared with prasugrel. Patient who entered the study before being on DAPT for 2 weeks will be required to complete 2 weeks of DAPT with aspirin and prasugrel/ticagrelor before randomization.

Blood sampling for PD testing will be conducted at 3 time-points: a) baseline (while patients will be on standard DAPT prior to initiating randomized treatment); b) after 7-10 days of randomized study treatment; c) after 30 ± 3 days of randomized study treatment. At each time point, blood will be collected before the morning dose of prasugrel/ticagrelor and vorapaxar, in order to measure trough levels of platelet inhibition. During study treatment in-hospital major adverse cardiac events (death, MI, stroke, and urgent revascularization procedures) and serious adverse events (bleeding and other adverse events) will be collected. Bleeding will be defined by the BARC (Bleeding Academic Research Consortium) definition [19].

After study completion, patients will resume antiplatelet treatment regimen at the discretion of the treating physician. A flow diagram of the study design is illustrated below.

Laboratory assessments

Peripheral venous blood samples (20 mL) will be drawn through a short venous catheter inserted into a forearm vein and collected in citrate, EDTA, and serum tubes as appropriate for assessments. The first 2-4 mL of blood will be discarded to avoid spontaneous platelet activation. Blood sampling for PD will be performed at 3 time points as indicated above in the study design section. Various PD assays will be performed as described below. Given the potential interplay between PAR-1 and P2Y₁₂ mediated signaling, assessments specific for both pathways will be conducted [11]:

1. Light transmittance aggregometry (LTA)
2. Thrombelastograph Coagulation Analyzer TEG 6s Series system (CORA[®] system)
3. Whole blood vasodilator-stimulated phosphoprotein (VASP)
4. Serum thromboxane B2

Description of laboratory assays

1) Light transmittance aggregometry (LTA): Platelet aggregation will be performed using LTA according to standard protocols. Blood will be collected in citrated (3.8%) tubes. LTA will be assessed using platelet rich plasma (PRP) by the turbidimetric method in a 2-channel aggregometer (Chrono-Log 490 Model, Chrono-Log Corp., Havertown) as previously described [20,21]. Platelet agonists will include AA (1 mM), collagen (3 μ g/ml), ADP (5 and 20 μ M), TRAP (15 μ M), and a combination of 2 μ g/ml collagen-related peptide + 5 μ M ADP + 15 μ M TRAP (CAT). The reagent cocktail CAT will allow to assess the overall platelet response to a combination of agonists that leads to activation of multiple platelet pathways. PRP will be obtained as a supernatant after centrifugation of citrated blood at 1000 rpm for 10 minutes. The isolated PRP will be kept at 37° C before use. Platelet poor plasma (PPP) will be obtained by a second centrifugation of the blood fraction at 2800 rpm for 10 minutes. Light transmission will be adjusted to 0% with the PRP and to 100% for the PPP for each measurement. Curves will be recorded for 6 minutes and platelet aggregation will be determined as the maximal percent change (MPA) in light transmittance from baseline using PPP as a reference.

2) TEG 6s Series system (CORA[®] system): the TEG 6s system (Haemonetics Corporation, Braintree, MA, USA) will be used according to manufacture instructions [22]. In brief, the CORA[®]

system is a new generation portable thrombelastography technology able to evaluate all phases of hemostasis, including time to clot formation, rate of clot formation, strength of clot and residual clot strength due to antiplatelet drugs, rate of clot lysis. Disposable assay cartridges contain all of the components necessary to allow the analyzer to prepare samples and perform hemostasis tests. The analyzer automatically draws the blood into the active area of the cartridge, meters the exact amount required for the test, and mixes it with the reagents spotted in the cartridge. The analyzer then monitors the harmonic motion of a pendant drop of blood in response to external vibration. As the sample transitions from a liquid state to a gel-like state during clotting, the modulus of elasticity and resonant frequency increase. The instrument measures these variations in resonant frequency during clotting and lysis. The results are displayed in a table and on a graphical tracing that reflects a hemostasis profile of clot formation. The resulting hemostasis profile is a measure of the time it takes for the first measurable clot to be formed, the kinetics of clot formation, the strength of the clot, and the breakdown of the clot, or fibrinolysis. In particular, the PlateletMapping Cartridge are used to assess platelet function in patients who have received platelet inhibiting drugs. The PlateletMapping assay consists of a set of agonists, ADP and arachidonic acid (AA) platelet agonists together with ActivatorF, which can measure the inhibition of platelet function. This assay specifically determines the MA (Maximum Amplitude, a measure of clot strength) and the reduction in MA due to antiplatelet therapy and reports it as a percentage of reduction in clot strength. The assay uses AA and ADP agonists to generate test results that reflect the inhibiting effects of antiplatelet agents such as TxA₂ Inhibitors (e.g., aspirin) and ADP P₂Y₁₂ inhibitors (e.g., ticagrelor). Since thrombin (present in blood samples) is the primary and most potent activator of platelets, its activity must be inhibited with heparin so that the platelet activating effects of ADP and

AA can be measured. Since thrombin has been rendered inactive by heparin, activatorF is used to replace thrombin's role in the conversion of fibrinogen to fibrin and Factor XIII to Factor XIIIa. Thus, with this cross-linked fibrin network as the foundation, additional clot strength due to platelet-fibrin bonding related to ADP and AA platelet receptor activation can be measured. The HKH reagent, a combination of kaolin and heparinase, generates test data for the uninhibited MA resulting from thrombin activation of the blood sample, while the heparinase neutralizes the effects of heparin. The HKH test provides measures of R (Reaction time; the amount of time between the start of the test and the beginning of coagulation), K (the speed of formation of the clot from R time to a specific clot strength), Angle (the speed of clot strengthening), LY30 (Percent lysis 30 minutes after MA is finalized) and MA parameters; The activatorF test provides the contribution of fibrin to the overall strength of the clot. This test value is used in the calculation of aggregation/inhibition for MA ADP and MA AA. The AA and ADP test provide measures of MA, percent inhibition and percent aggregation.

3) Whole blood vasodilator-stimulated phosphoprotein (VASP): VASP phosphorylation (VASP-P) is a marker of P2Y₁₂ receptor reactivity. VASP will be assessed according to standard protocol using labeled monoclonal antibodies by flow cytometry with the Platelet VASP-FCM kit (Biocytex Inc., Marseille, France) as previously described [23]. PGE1 increases VASP-P levels by stimulation of adenylate cyclase. Binding of ADP to P2Y₁₂ leads to Gi-coupled inhibition of adenylate cyclase. Therefore, the addition of ADP to PGE1-stimulated platelets reduces PGE1-induced VASP-P levels. If P2Y₁₂ receptors are successfully inhibited by inhibitors, addition of ADP will not reduce the PGE1-stimulated VASP-P levels. The platelet reactivity ratio (PRI) will be calculated after measuring VASP-P levels after stimulation with PGE1 (MFI PGE1) and also PGE1 + ADP (MFI

PGE1 + ADP). The P2Y12 reactivity ratio = $([\text{MFI PGE1}] - [\text{MFI PGE1} + \text{ADP}]) / [\text{MFI PGE1}] \times 100\%$.

4) Serum thromboxane B2: The concentration of serum thromboxane B2 (TXB2) will be measured by using the TXB2 EIA kit (Cayman Chemical Company, Ann Arbor, MI) according to the instructions of the manufacturer, as previously described [24]. Briefly, samples will be diluted with EIA buffer to bring their concentrations within the range of the standard curve. No other purification will be performed on any of the samples. A standard curve will be established by serial dilution of TXB2 between 1000 pg/mL and 7.8 pg/mL using EIA buffer as the matrix. The concentration of TXB2 in the samples will be calculated from a logistic 4-parameter fit of the standard concentrations versus percentage bound/maximum bound.

Study endpoints and sample size calculation

The primary end point of our study is the comparison of CAT-induced MPA between DAPT and DAPT plus vorapaxar after 30 ± 3 days of treatment. We hypothesize that adjunctive vorapaxar will result into a significant reduction of platelet aggregation. Assuming a 10% absolute reduction in CAT-induced MPA with a common standard deviation of 13%, 37 patients per group will be needed to detect a significant difference between DAPT and DAPT plus vorapaxar with a 90% power and 2-sided $\alpha=0.05$. Considering a possible 30-35% rate of invalid results due to hemolysis or drop-out and the three arms of treatment up to 146 patients will need to be randomized. Since there are no preliminary data in this particular setting, the sample size of our study was calculated based on previous data of vorapaxar in addition to DAPT with aspirin and clopidogrel [21]. This approach is in agreement with recommendations for pilot investigations [25].

Our secondary outcome will be the comparison of CAT-induced MPA between vorapaxar in addition to a new generation P2Y₁₂ receptor inhibitor (prasugrel or ticagrelor) and vorapaxar in addition to standard DAPT (aspirin and prasugrel/ticagrelor). We hypothesize that stopping aspirin will not lead to significant differences in CAT-induced MPA after 30 ± 3 days of treatment.

Other objectives will include the comparisons among the 3 groups of all PD parameters measured by multiple assays at every time point, as well as intragroup comparisons of PD parameters in order to evaluate the variability over time of vorapaxar PD effects, as well as how PD measures will be affected by aspirin withdrawal.

Statistical analysis plan

Categorical variables will be expressed as frequencies and percentages. Continuous variables will be presented as mean \pm SD or median [IQR]. Continuous variables will be analyzed for normal distribution with the Kolmogorov-Smirnov test. Comparisons between categorical variables will be performed using two-tailed Fisher's exact test or the Pearson's chi-square test. Student's t test, Mann-Whitney U-test and Wilcoxon test will be used to compare continuous variables when appropriate. An analysis of covariance (ANCOVA) method with a general linear model, using baseline variables significantly different between groups as covariates, will be used to evaluate the overall difference between groups and all between-groups comparisons, in line with other PD studies [23]. Analysis of variance (ANOVA) will be used to evaluate intragroup comparisons. A 2-tailed p value of < 0.05 is considered to indicate a statistically significant difference for all the analyses performed. Statistical analysis will be performed by our group using SPSS v22.0 software (SPSS Inc. Chicago, IL).

Publication Strategy/Additional Information

Study subjects will be identified first (months 1-24): we expect to enroll approximately 5-6 subjects monthly and complete enrollment in 24 months (total: 126 subjects enrolled). Months 25-26 will be implied for statistical analysis and months 27-28 for manuscript preparation. We intend to present data at a major scientific meeting at completion of the study.

We anticipate no major problems with the described protocol since the approach is a straight forward prospective study and is based on well-established methods. However, since there is limited experience with vorapaxar to define platelet function, variability may be higher than expected and we cannot currently perform a detailed sample size calculation. We anticipate adding this to the protocol after inclusion of the study population has been completed. If the sample size after one year is estimated to be too small, additional patients will be included. This approach is in agreement with recommendations for pilot investigations [25].

Possible Discomforts and Risk

In clinical trials, the most common clinical side effects of vorapaxar were anemia (5%), depression (2.4%) and rash (2.2%) [14, 18]. The most important adverse effect associated with the use of vorapaxar is bleeding. The risk of TIMI clinically significant bleeding with vorapaxar is 15.8% and 11.1% with placebo (HR 1.46; 95% CI, 1.36-1.57, $p < 0.001$); the risk of TIMI non-CABG-related major bleeding with vorapaxar is 2.8% and 1.8% with placebo (HR 1.46; 95% CI, 1.22-1.75, $p < 0.001$); the risk of intracranial bleeding (intracerebral, subdural or epidural) with vorapaxar is 1% vs 0.5% with placebo (HR 1.94; 95% CI 1.39-2.70; $p < 0.001$) [14]. However, such

bleeding prevalence occurred in the setting of long-term (3 years) trial, while our study is limited to only approximately 30 days of vorapaxar therapy. We have also excluded from the study patients at increased risk of bleeding complications [12-14]. Moreover, the use of vorapaxar in this study is limited to the intended for use population at low risk of bleeding. All clinical events described above, if they were to occur, as well as death, myocardial infarction, stroke, and urgent revascularization procedure with PCI or coronary artery bypass grafting will be recorded. Bleeding data will be collected using BARC definitions [20]. Clinical events will be evaluated by a local committee, comprised of 2 faculty members (2 cardiologists), not directly involved in the research. In the event of a report of a serious adverse event (major bleeding – defined as life-threatening: fatal, symptomatic intracranial hemorrhage, leading to a drop in hemoglobin of at least 5 g/dL, significant hypotension requiring intravenous inotropes, requiring surgical intervention, or requiring transfusion of 4 or more units of blood; non–life-threatening: substantially disabling, intraocular bleeding leading to vision loss, or requiring at least 2 units of blood; thrombocytopenia <50,000) the local committee will meet and antiplatelet treatment management will be managed according to physician recommendation.

Definition of Adverse Events

An adverse event is any unintended or undesirable experience that occurs during the course of the clinical investigation whether or not it is considered to be therapy related. This includes any newly occurring event or previous condition that has increased in severity or frequency since the initiation of study treatment. Adverse events will be followed until resolution while the patient

remains on-study. Once the patient is removed from study, events thought to be related to the study therapy will be followed until resolution or until the patient starts a new treatment regimen.

Serious Adverse Events (SAE): An adverse event occurring while on study and considered related (reasonable possibility that the study treatment caused the adverse experience) to the study treatment that results in any of the following outcomes:

- Death
- A life-threatening adverse experience.
- A persistent or significant disability, incapacity, or is a congenital anomaly, or birth defect.
- Requires inpatient hospitalization, or prolongation of existing hospitalization.

The definition of serious adverse event also includes ‘important medical event’. Medical and scientific judgment should be exercised in deciding whether expedited reporting is appropriate in other situations, such as important medical events that may not be immediately life-threatening or result in death or hospitalization but may jeopardize the patient and/or may require medical or surgical intervention to prevent one of the other outcomes listed in the definition above. These should also usually be considered serious. Examples of such events are intensive treatment in an emergency room or at home for allergic bronchospasm; blood dyscrasias or convulsions that do not result in hospitalization; or development of drug dependency or drug abuse.

Possible benefits

The present investigation is aimed to evaluate the PD effects of vorapaxar as an add-on therapy to standard antiplatelet treatment in patients with previous MI. This study is not designed to evaluate differences in clinical benefit. However, differences in antiplatelet profiles may potentially prompt further investigations of the clinical implication of this difference by means of a larger scale clinical study.

Potential Financial Risks or Benefits

None

Conflict of Interest

[name] is a consultant for Merck, the maker of vorapaxar.

References

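### Randomisation is stratified by P2Y12 inhibitor, but the planned ANCOVA will almost always omit the stratum and no by-drug estimate is planned

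*Combined protocol and SAP*

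**What the plan says.** All references are to the combined protocol and SAP.

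- **Research Design, allocation.** Patients are "randomly assigned in a 1:1:1 fashion to one of the following 3 treatment regimens": (1) DAPT plus vorapaxar, (2) prasugrel or ticagrelor plus vorapaxar without aspirin, (3) DAPT alone. "Randomization will be stratified according to type of" P2Y12 inhibitor, "in order to include at least 35% of patients on prasugrel".
- **Study endpoints and sample size calculation.** The primary endpoint compares CAT-induced maximal platelet aggregation (CAT-MPA) "between DAPT and DAPT plus vorapaxar after 30 ± 3 days of treatment". The secondary outcome compares arm 2 with arm 1, with the hypothesis that stopping aspirin makes no significant difference. The other objectives compare the three arms and look at changes within arms. All of them pool prasugrel and ticagrelor.
- **Statistical analysis plan.** Between-group comparisons use an ANCOVA, "using baseline variables significantly different between groups as covariates". The section names no stratum term, by-drug estimate or drug-by-treatment term.

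**The concern.** When randomisation is stratified, the arms are balanced on the stratifier by design, so any outcome variation due to it no longer contributes to the true variance of the arm contrast. An analysis that ignores the stratifier leaves that variation in the residual and reports a standard error that is too large.

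The covariate rule makes this the expected result here. A factor that is balanced by stratification should not differ significantly between arms, so it would enter the model only by accident, for example after uneven loss of samples.

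The two comparisons are affected differently. In the primary comparison an overstated standard error wastes some power. In the secondary comparison the hoped-for result is non-significance, and an overstated standard error makes that slightly easier to reach.

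Separately, the trial collects patients on two background drugs with a set minimum for one of them, yet plans no estimate on either. A by-drug look taken later would be post hoc.

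**Working it through.** **Inputs from the documents.** Difference 10 points, SD 13, 37 evaluable per arm, 90% power, two-sided alpha 0.05, prasugrel share at least 35%, loss 30-35%, up to 146 randomised (sample-size section) or 126 enrolled (timeline under Publication Strategy/Additional Information).

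**Assumptions.** The documents give no difference in CAT-MPA between drugs, so d = 0, 5 and 10 points are used to show the range. The share is set at the 35% minimum and taken as equal in every arm. The stratification is assumed to achieve balance.

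**1. The plan's own figure.** The plan states: "Assuming a 10% absolute reduction in CAT-induced MPA with a common standard deviation of 13%, 37 patients per group will be needed". The normal approximation gives n = 2 × (1.960 + 1.282)² × 13² / 10² = 35.5, so 36. The t-test gives 36.5, so 37. Power at 37 per arm is 0.904 by t-test. The stated figure reproduces for the pooled comparison.

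**2. Effect of omitting the stratum.** Variance between drugs = 0.35 × 0.65 × d² = 0.2275 d². Its share of the total is R² = 0.2275 d² / 169, and the reported standard error is too large by a factor of 1/√(1 − R²).

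| d (assumed) | Between-drug variance | R² | SE overstated by |
|---|---|---|---|
| 0 | 0 | 0 | 0 |
| 5 | 5.7 | 3.4% | 1.7% |
| 10 | 22.8 | 13.5% | 7.5% |

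For the primary contrast the unadjusted standard error is 13 × √(2/37) = 3.02 points. With the stratum removed from the residual it is 3.02 × √(1 − R²) = 2.97 (d = 5) or 2.81 (d = 10).

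**3. Precision of by-drug estimates.** At 35%, 37 per arm is about 13 on prasugrel and 24 on ticagrelor.

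- Prasugrel: SE = 13 × √(2/13) = 5.10; half-width 1.96 × 5.10 = 10.0.
- Ticagrelor: SE = 13 × √(2/24) = 3.75; half-width 7.4.
- Difference in effect: SE = √(5.10² + 3.75²) = 6.33; half-width 12.4.

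Fewer evaluable patients widen these:

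| Evaluable per arm | Prasugrel / ticagrelor | Half-width, prasugrel | Half-width, ticagrelor | Half-width, difference in effect |
|---|---|---|---|---|
| 37 (plan) | 13 / 24 | 10.0 | 7.4 | 12.4 |
| 34 (146, 30% lost) | 12 / 22 | 10.4 | 7.7 | 12.9 |
| 32 (146, 35% lost) | 11 / 21 | 10.9 | 7.9 | 13.4 |
| 29 (126, 30% lost) | 10 / 19 | 11.4 | 8.3 | 14.1 |
| 27 (126, 35% lost) | 9 / 18 | 12.0 | 8.5 | 14.7 |

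Step 3 treats 13 as the within-drug SD, while step 2 treats it as the total SD. If 13 is the total and d = 10, the within-drug SD is √(169 − 22.75) = 12.1 and every half-width shrinks by about 7%. The picture does not change.

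**4. What by-drug data could detect.** At 37 per arm, power for a 10-point effect is 47-50% on prasugrel and 74-76% on ticagrelor (t-test and normal approximation). Power for a 10-point difference in effect, which would be complete loss of the assumed effect on one drug, is about 35%. The difference detectable with 80% power is (1.960 + 0.842) × 6.33 = 17.7 points, more than the assumed main effect.

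**The case against.** The strongest reply is that the plan answers the aim it states. Study Aims is worded for the class, a new-generation P2Y12 inhibitor of either kind, and the stated purpose of stratifying is the prasugrel share. A pooled comparison meets that aim. This stands.

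Three stronger readings are tempting, and the documents do not support them.

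- *A reader might infer from the title, which names both drugs, that the trial promises to show the effect on each.* No objective or hypothesis says so.
- *A reader might infer that the prasugrel minimum serves no purpose without a by-drug analysis.* It keeps the pooled result from being nearly all ticagrelor, and stratification balances the background drug across arms. Both benefits remain.
- *A reader might infer that the drugs behave differently on this endpoint, because trough sampling falls about 24 hours after a once-daily drug and about 12 hours after a twice-daily one.* That shows different intervals since the last dose, not different CAT-MPA. No such difference is reported in the documents, and Study Rationale describes the two drugs together as effective on the same pathways.

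It is also fair to say that the standard-error cost is small and conservative for the primary comparison. At 5 points it is 1.7%, and the 10-point case assumes a drug difference as large as the whole hypothesised vorapaxar effect. This too stands. It limits the size of the point, but does not explain why the randomisation stratum should be left to a baseline significance test.

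**Conclusion.** The point holds as an inexpensive improvement to the analysis, not as a threat to validity. The stratifier is absent from the model, the covariate rule will almost always keep it out, and no by-drug estimate is planned. The arm contrast is not biased. Its standard error is overstated by between nothing and about 7.5% over the assumed range of 0 to 10 points between drugs. This costs a little power in the primary comparison and slightly favours a non-significant secondary result. The size depends on a between-drug difference that the documents do not give. The absence of the stratum and of by-drug estimates does not.

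By-drug estimates would be worth reporting but could not settle consistency: with about 35% power for a 10-point difference in effect, even complete loss of effect on one drug would usually go undetected.

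**What to change.** - **Statistical analysis plan.** Include P2Y12 inhibitor (prasugrel or ticagrelor) as a fixed factor in the ANCOVA for the primary and secondary comparisons, regardless of any baseline test.
- **Study endpoints and sample size calculation.** Add to the other objectives the arm 1 versus arm 3 and arm 2 versus arm 1 differences in CAT-MPA within each drug, and the drug-by-treatment difference for each contrast, all with 95% confidence intervals and labelled descriptive.
- **Same section.** State that these estimates are imprecise (half-widths of about 10, 7.4 and 12.4 points at 37 evaluable per arm, wider if fewer are evaluable) and that they can neither establish nor rule out a consistent effect.

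The cost is one degree of freedom in the main model, two more in the separate descriptive interaction model, and one table. No extra patients, visits or assays are needed.
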